## HO: $\Delta$ FBFRiva $\leq \Delta$ FBFASS H1: $\Delta$ FBFRiva $> \Delta$ FBFASS

- Type I error:  $\alpha$  = 0.05, one-tailed t-test for independent samples
- Power: 1-ß = 0.90
- Estimated dropout rate : 25 %
- Minimum of expected clinical relevant difference between the groups in changes of maximal forearm blood flow ( $\Delta$ FBF) = 1.2 ml/100ml with an estimated standard deviation (SD) of  $\sigma$  = 2.4 ml/100ml [Pistrosch, F. et al. Diabetes Care 27: 484-490, 2004]

Sample size should be N = 188 Patients ( $N_{1/2}$  = 94 patients per arm) for a valid number of 141 patients for per protocol analysis. This sample size may also provide enough power for further analyses.

Additionally, the second primary variable is difference of PWV between treatment groups at EOT Extension (after 52 week of treatment). The sample size calculation is based on the following assumptions:

H0: PWVRiva=PWVASS

H1: PWVRiva≠PWVASS

- Type I error:  $\alpha$  = 0.05, t-test for independent samples

- Power: 1-ß = 0.80
- Estimated dropout rate : 20 %
- Minimum of expected clinical relevant difference between the groups in PWV = 0.7 m/s with an estimated standard deviation (SD) of  $\sigma$  = 1.0 m/s

Sample size should be N=80 patients (40 patients per arm) for a valid number of 66 patients for per protocol analysis.

In summary the necessary sample size would be N=188 patients for the study up to week 20 including 80 patients for the extension up to week 52.

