## 9.2 Statistical methods

Descriptive or summary statistics will be displayed for continuous data and for categorical data. All continuous variables will be summarised using the following statistics: n (non-missing sample size), mean, 95 % confidence interval, standard deviation, median, maximum and minimum. The frequency and percentages (based on the non-missing sample size) of observed levels will be reported for all categorical measures. In general, all data will be listed, sorted by subject and visit number. All summary tables will be annotated with the total population size relevant to that table/treatment, including any missing observations.

Comparisons will be tested at the 2-sided 5% significance level. For the primary study endpoint, a one-sided significance level of 5% will be assumed.

T-tests for independent samples will be used for single comparisons between treatment arms (like the primary study endpoint). Analyses of the continuous variables over time will be performed as paired t-Test, repeated measures analysis of variance or mixed models. All analyses of categorical measures will be performed using Fisher's exact test, McNemar's Test or  $\chi^2$  test. Previous correlation analyses of outcome variables and possible predictors will provide evidence for inclusion in analysis. In this trial, most relevant time points for analyses of longitudinal data for secondary study endpoints are at baseline (V1) and after end of treatment (V6).

Individual listings of treatment-emergent adverse events will be provided. The incidence of treatment-emergent adverse events, respectively, will be summarized using WHO SOC terms. Analysis of adverse events will be based on the safety analysis set.

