#### 2.4 Sample size calculation

The first primary variable is the change of forearm blood flow with venous occlusion plethysmography ( $\Delta$ FBF) after forearm ischemia after 20 weeks of treatment. The sample size calculation is based on the following assumptions:

- Hypotheses: H0:  $\mu_{\Delta FBF, Riva} \leq \mu_{\Delta FBF, ASS}$ H1:  $\mu_{\Delta FBF, Riva} > \mu_{\Delta FBF, ASS}$
- Application of t-test for independent samples
- Type I error:  $\alpha = 0.05$
- Power: 1-ß = 0.90
- Estimated dropout rate: 25 %
- Minimum of expected clinical relevant difference between the groups in changes of maximal forearm blood flow ( $\Delta$ FBF) = 1.2 ml/100ml with an estimated standard deviation (STD)  $\sigma$  = 2.4 ml/100ml

Sample size should be at least N = 188 Patients (i.e. N/2 = 94 patients per arm) in order to achieve a valid number of 141 patients (per protocol analysis).

Additionally, the second primary variable is the difference of PWV between treatment groups at EOT Extension (after 52 week of treatment). The sample size calculation is based on the following assumptions:

H0: μPWV, Riva = μPWV, ASS

• H1:  $\mu_{PWV, Riva} \neq \mu_{PWV, ASS}$ 

• Type I error:  $\alpha = 0.05$ , t-test for independent samples

• Power: 1-ß = 0.80

Estimated dropout rate: 20 %

• Minimum of expected clinical relevant difference between the groups in PWV = 0.7 m/s with an estimated standard deviation (STD) of  $\sigma$  = 1.0 m/s

Sample size should be N=80 patients (40 patients per arm) to achieve a valid number of 66 patients for per protocol analysis.

In summary the necessary sample size would be N=188 patients for the study up to week 20 including 80 patients for the extension up to week 52.

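### Week-52 PWV sample size: 80 patients entering the extension less the stated 20% dropout leaves 64 evaluable, not the stated 66; the effect on power is about one percentage point.

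*Protocol*

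**What the plan says.** Protocol section 9.1.8 lists the assumptions for the week-52 PWV comparison:

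- a two-sided alternative, "H1: PWV Riva ≠PWV ASS"
- a type I error of "0.05, t-test for independent samples"
- "Power: 1-ß = 0.80"
- "Minimum of expected clinical relevant difference between the groups in PWV = 0.7 m/s", with an SD of 1.0 m/s
- "Estimated dropout rate : 20" per cent

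The list ends: "Sample size should be N=80 patients (40 patients per arm) for a valid number of 66 patients for per protocol analysis". The statistical methods part of the synopsis repeats it. SAP section 2.4 carries the same inputs and the same result: "Sample size should be N=80 patients (40 patients per arm) to achieve a valid number of 66 patients for per protocol analysis".

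The FBF calculation, also in section 9.1.8, assumes 25% dropout and goes from 188 patients to 141 evaluable. Protocol sections 4.2 and 9.1.8 make clear that 188 patients are randomised and that the 80 are the subset who continue into the extension.

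**The concern.** The three PWV figures (80 patients, 20% dropout, 66 evaluable) do not fit together when dropout is taken as the share of enrolled patients who are lost. PWV at week 52 is named as a primary variable for the extension, so its evaluable number and its power are stated design properties. As written, the plan gives two evaluable targets, 66 as stated and 64 as implied. It also gives two dropout assumptions, 20% as stated and 17.5% as implied. Anyone who later compares the achieved numbers with the plan cannot tell which one applies. The SAP repeats the line, so it does not settle the matter.

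**Working it through.** **Inputs** (protocol 9.1.8; the same in SAP 2.4): difference δ = 0.7 m/s, SD σ = 1.0 m/s, α = 0.05, power 0.80, equal arms, dropout 20%, N = 80. The test is taken as two-sided because the alternative is a non-equality. Protocol 9.2 also says "Comparisons will be tested at the 2-sided 5% significance level". Its one-sided exception is for the primary study endpoint, and SAP 6.11.1 makes only the FBF test one-sided.

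**Step 1. Reproduce the 66.** By the normal approximation,

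n per arm = 2 × ((1.960 + 0.842) × σ/δ)² = 2 × (2.802/0.7)² ≈ 32.04, rounded up to 33.

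Two arms give 66, the plan's figure. A one-sided test would need only 26 per arm, which does not fit. So 66 is the number of evaluable patients required for 80% power.

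**Step 2. Apply the dropout.**

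- 80 × (1 − 0.20) = 64, or 32 per arm if losses are equal.
- Dropout implied by 66 of 80: 1 − 66/80 = 17.5%.
- Entrants needed to keep 66 after 20% loss: 66/0.80 = 82.5, so 83, or 84 with equal arms.

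**Step 3. Check which convention the plan uses.** For FBF, 188 × (1 − 0.25) = 141 exactly, and 141/0.75 = 188. The other convention, multiplying the evaluable number by one plus the dropout rate, would give 141 × 1.25 = 176.25, which is not 188.

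**Step 4. Power at each evaluable number.** For the t-test the noncentrality is (δ/σ) × √(n/2), with 2n − 2 degrees of freedom. At n = 32 it is 0.7 × √16 = 2.80.

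| Evaluable per arm (total) | Power, noncentral t | Power, normal approximation |
|---|---|---|
| 32 (64) | 78.7% | 79.96% |
| 33 (66) | 79.97% | 81.2% |
| 34 (68) | 81.2% | 82.3% |

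Under the named t-test, 64 instead of 66 costs 79.97 − 78.71 = about 1.3 percentage points.

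**The case against.** **The 80 may come from a different inflation.** 66 × 1.2 = 79.2, rounded up to 80, would link all the stated figures. This may well be how the 80 arose, and if so the slip lies in the step from 66 to 80 and not in the 66 itself. The documents do not state the inflation formula, however. The FBF line in the same section follows the other rule, and a 20% loss from 80 still leaves 64. The inconsistency stands.

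**The stated power is hardly affected.** This is right, and it limits the point. A reader might infer that the extension fails to deliver its 80% power and is underpowered for PWV. The documents do not support that:

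- By the normal approximation, 64 evaluable gives 79.96%.
- Under the t-test, even the plan's own 66 gives 79.97%, which reaches 80% only by rounding.
- The t-test may not be the final analysis. The synopsis names ANCOVA for the primary parameters. SAP 6.11.1 refers PWV to the procedure for continuous data, which SAP 6.3 defines as ANCOVA with the baseline value as covariate when normality is not rejected.

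The documents give no correlation between baseline and week-52 PWV, so any gain from adjustment rests on an assumption. With residual SD σ√(1 − r²), 64 evaluable and 61 degrees of freedom, power is 79.1% at r = 0.1, 80.3% at r = 0.2, 82.3% at r = 0.3 and 88.9% at r = 0.5. The gap closes at roughly r = 0.2.

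**The same sentence appears three times, so this is one slip.** Agreed. The repetition matters only because all three places need the correction.

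**Conclusion.** The dropout step of the PWV calculation is wrong as written: the plan's own inputs leave 64 evaluable patients, not 66. The arithmetic uses only stated figures and assumes that the 20% applies to the 80 patients entering the extension. The power figure further assumes equal losses in the two arms and the named two-sided 5% t-test. On that basis power is 78.7% instead of 80.0%, a difference of two patients and about 1.3 points. This is a minor inconsistency to tidy, not a material power failure. No endpoint, analysis set or decision rule changes.

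**What to change.** In protocol 9.1.8, the synopsis and SAP 2.4, restate the result as 80 patients entering the extension, 20% dropout, 64 evaluable (32 per arm), power about 79% by two-sided t-test. The wording should say entering the extension and not randomised, because 188 patients are randomised.

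The cost is one corrected line in three places and a slightly less favourable stated power. No extra patients are needed. If the sponsor prefers to keep both 66 evaluable and 20% dropout, 83 patients (84 with equal arms) would have to enter the extension, three or four more than planned. Changing the dropout assumption to 17.5% would make the figures agree, but it only fits the assumption to the total, and nothing in the documents supports that rate.

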## 9.2 Statistical methods

Descriptive or summary statistics will be displayed for continuous data and for categorical data. All continuous variables will be summarised using the following statistics: n (non-missing sample size), mean, 95 % confidence interval, standard deviation, median, maximum and minimum. The frequency and percentages (based on the non-missing sample size) of observed levels will be reported for all categorical measures. In general, all data will be listed, sorted by subject and visit number. All summary tables will be annotated with the total population size relevant to that table/treatment, including any missing observations.

Comparisons will be tested at the 2-sided 5% significance level. For the primary study endpoint, a one-sided significance level of 5% will be assumed.

T-tests for independent samples will be used for single comparisons between treatment arms (like the primary study endpoint). Analyses of the continuous variables over time will be performed as paired t-Test, repeated measures analysis of variance or mixed models. All analyses of categorical measures will be performed using Fisher's exact test, McNemar's Test or  $\chi^2$  test. Previous correlation analyses of outcome variables and possible predictors will provide evidence for inclusion in analysis. In this trial, most relevant time points for analyses of longitudinal data for secondary study endpoints are at baseline (V1) and after end of treatment (V6).

Individual listings of treatment-emergent adverse events will be provided. The incidence of treatment-emergent adverse events, respectively, will be summarized using WHO SOC terms. Analysis of adverse events will be based on the safety analysis set.

## 10 Safety

## 10.1 Definitions of adverse events and adverse drug reactions

### 10.1.1 Adverse event

An adverse event (AE) is any untoward medical occurrence (i.e. any unfavorable and unintended sign [including abnormal laboratory findings], symptom or disease) in a patient or clinical investigation subject after randomization /first intake of study medication in the study. Therefore, an AE may or may not be temporally or causally associated with the use of a medicinal (investigational) product.

A surgical procedure that was planned prior to the start of the study by any physician treating the subject should not be recorded as AE (however, the condition for which the surgery is required may be an AE).

In the following differentiation between medical history and AEs, the term "condition" may include abnormal e.g. physical examination findings, symptoms, diseases, or laboratory or ECG test results.

- Conditions that started before signing of informed consent and for which no symptoms or treatment are present until signing of informed consent are recorded as medical history (e.g. seasonal allergy without acute complaints).
- Conditions that started before signing of informed consent and for which symptoms or treatment are present after signing of informed consent, at unchanged intensity, are recorded as medical history (e.g. allergic pollinosis).
- Conditions that started or deteriorated after signing of informed consent will be documented as adverse events.

### 10.1.2 Adverse drug reaction

An adverse drug reaction (ADR) is any noxious and unintended response to an IMP related to any dose with at least a reasonably possible causal relationship with the IMP.

### 10.1.3 Serious adverse events and serious adverse reactions

A serious adverse event (SAE) or serious adverse drug reaction (SADR) is classified as any untoward medical occurrence that, at any dose, meets any of the following criteria (a - f):

- results in death
- is life-threatening

The term 'life-threatening' in the definition refers to an event in which the patient was at risk of death at the time of the event, it does not refer to an event which hypothetically might have caused death if it were more severe.

requires inpatient hospitalization or prolongation of existing hospitalization

A hospitalization or prolongation of hospitalization will not be regarded as an SAE if at least one of the following exceptions is met:

- the admission results in a hospital stay of less than 12 hours
- the admission is pre-planned(i.e. elective or scheduled surgery arranged prior to the start of the study that is written in the patient / study file)
- the admission is not associated with an AE (e.g. social hospitalization for purposes of respite care)

However, it should be noted that invasive treatment during any hospitalization may fulfill the criterion of 'medically important' and as such may be reportable as an SAE dependent on clinical judgment. In addition, where local regulatory authorities specifically require a more stringent definition, the local regulation takes precedence.

- results in persistent or significant disability / incapacity
   Disability means a substantial disruption of a person's ability to conduct normal life's functions.
- is a congenital anomaly / birth defect
- is another medically important serious event as judged by the investigator

If an AE is classified as an SAE, this is documented on a separate SAE sheet in addition to the standard AE documentation.

## 10.1.1 Unexpected adverse drug reaction

An unexpected ADR is an ADR for which the nature or severity is not consistent with the applicable product information available for the IMP. Expected ADRs are listed in the appropriate reference document, i.e. in the SmPC.

### 10.1.2 Suspected unexpected serious adverse reactions

A suspected unexpected serious adverse reaction (SUSAR) is an adverse event for which the nature or severity is not consistent with the product information available for the IMP, is regarded as serious, and has at least a possible causal relationship with the IMP.

## 10.2 Documentation and follow-up of adverse events

The sponsor ensures that all persons involved in the treatment of trial subjects are adequately informed about the responsibilities and actions required when AEs occur. Trial subjects will be

asked at each visit whether they have experienced AEs or SAEs. AEs will be documented in the trial subject's medical records and in the eCRF.

For the procedure of SAE-reporting see section 10.3.

## 10.2.1 Classifications for adverse event assessment

All AE/SAE will be assessed and documented by the investigator according to the categories detailed below.

#### SERIOUSNESS

For each AE, the seriousness must be determined according to the criteria given in section 10.2.1

#### INTENSITY

The intensity of an AE is classified according to the following categories, taking into account the possible range of the intensity of the event: mild, moderate, severe.

#### CAUSAL RELATIONSHIP

The assessment of the causal relationship between an AE and the administration of treatment is a clinical decision based on all available information at the time of the completion of the eCRF. The assessment is based on the question whether there was a "reasonable causal relationship" to the study treatment in question.

For the assessment of the causal relationship to medication following points should be considered:

- laboratory test abnormalities which cannot be explained by concurrent disease or other drugs or chemicals
- the response to withdrawal of the drug (dechallenge) and rechallenge information events in a reasonable time sequence to administration of the drug rechallenge

Possible answers for an assessment of relationship are "yes" or "no".

An ADR/SADR is suspected if the causal relationship is assessed as "yes". Events assessed as "no" are not suspected ADRs/SADRs.

### 10.2.2 Causal relationship to protocol-required procedure(s)

The assessment of a possible causal relationship between the AE and protocol-required procedure(s) is based on the question whether there was a "reasonable causal relationship" to protocol-required procedure(s).Possible answers are "yes" or "no"

#### ACTION TAKEN WITH STUDY TREATMENT

Any action on study treatment to resolve the AE is to be documented using the following categories: drug withdrawn, drug interrupted, dose reduced, dose not changed, dose increased, not applicable, unknown.

#### OTHER SPECIFIC TREATMENT(S) OF ADVERSE EVENTS

- None
- Remedial drug therapy
- Other

#### OUTCOME

The outcome of all events is to be documented as follows: recovered/resolved, recovered/resolved with sequelae, not recovered/not resolved, life-threatening, fatal, unknown

### 10.2.3 Assessments and documentation of adverse events

AEs observed, mentioned upon open questioning by a member of the investigator's team or spontaneously reported by the subject will be documented. The observation phase for AEs will start with randomization / first intake of study medication and will end in general with the last visit. In case of ongoing AEs after the last follow-up visit – especially when related to treatment with the study medication – the respective AE will be followed until resolution, if possible. The investigator is responsible for the grading of each category mentioned in section 10.2.1.

For all SAEs the sponsor has to carry out a separate assessment for expectedness, seriousness and causal relationship to treatment with the study medication.

## 10.3 Reporting of serious adverse events

### 10.3.1 Investigator's notification of the sponsor

The definition of SAEs is given in section 10.1. All investigators will be thoroughly instructed and trained on all relevant aspects of the investigator's reporting obligations for SAEs. This information, including all relevant contact details, is summarized in the ISF. This information will be updated as needed.

All SAEs occurring during the study (Screening to EOT) defined in Section 10.1.3 must immediately (within 24 hours of the investigator's awareness) be reported to the sponsor detailed in the manual. An SAE form must also be completed within 24 hours of the investigator awareness and forwarded to the sponsors safety management. Each SAE must be followed up until resolution or stabilization by submission of updated reports to the designated recipient.

SAEs occurring after the protocol-defined observation period will be processed by the sponsor according to all applicable regulations.

All SAEs must be sent via Fax or eMail to:

## GWT GmbH [name] Germany - 01307 Dresden [contact] eMail: [contact]

#### NOTIFICATION OF THE IECS / IRBS

Notification of the IECs / IRBs about all relevant events (e.g. SAEs, suspected, unexpected, serious adverse reactions (SUSARs)) will be performed by the sponsor and / or by the investigator according to all applicable regulations if requested by the sponsor.

#### NOTIFICATION OF THE AUTHORITIES

The processing and reporting of all relevant events (e.g. SAEs, SUSARs) to the authorities will be done by the sponsor according to all applicable regulations.

### SPONSOR'S NOTIFICATION OF THE INVESTIGATIONAL SITE

The sponsor will inform all investigational sites about reported relevant events (e.g. SUSARs) according to all applicable regulations.

#### NOTIFICATION OF THE MARKETING AUTHORIZATION HOLDER

The sponsor will also inform the marketing authorization holder about all SAEs and all SUSARs including information reported to the competent supreme authority and ethics committee in accordance with contractual agreements.

## 10.4 Expected adverse events

### 10.4.1 Adverse events possibly related to the study medication

For this study, the applicable reference document is the most current version of the SmPC. If relevant new safety information is identified, the information will be integrated into an update of the SmPC and distributed to all participating sites.

The expectedness of AEs will be determined by the sponsor according to the applicable reference document and according to all local regulations.

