## 5.3 Description of the IMP – Aspirin (ASS 100) (control group)

The IMP ASS 100 TAH of the control group will be preferably used from ratiopharm GmbH. If it becomes necessary (from indefinable reasons), instead of ratiopharm, Aspirin® Bayer or ASS 100 mg of HEXAL can be used as a control IMP in the same dosage. Both medications have an identical authorization profile.

Trade name:	ASS-ratiopharm ® 100 mg TAH
INN (International Nonproprietary Name)	acetylsalicylic acid
Galenical form / formulation	film coated tablet (white, round table with one-sided cross)
Strength	100 mg
Further contents	cellulose
Type of packaging and content	cartons of 50 tablets
Manufacturer	ratiopharm GmbH
Marketing authorization holder	ratiopharm GmbH

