## 5.10 Blinding

Not applicable, open-label study.

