#### SUMMARY OF THE SAFETY PROFILE

The majority of adverse reactions reported for Xarelto® 2.5 mg (Rivaroxaban) (respectively 10 mg daily dose) are bleeding complications (gastrointestinal bleeding, etc.).

Less frequently reported, but more serious, adverse reactions include anemia, allergic reaction, dizziness, headache, hematoma, hypotonia which are listed in the table below. The adverse

reactions are listed by system organ class and frequency using the following convention: very common ("1/10), common ("1/100 to < 1/10), uncommon ("1/1.000 to < 1/100), rare ("1/10.000 to < 1/1.000), very rare (< 1/10.000), not known (cannot be estimated from the available data). Within each frequency grouping, adverse reactions are presented in order of decreasing seriousness.

Blood and lymp	hatic system disorders
Common	anemia
Uncommon	thrombocythemia
Immune system	n disorders
Uncommon	allergic reaction, allergic dermatitis
Nervous system	n disorders
Common	dizziness, headache, syncope
Uncommon	cerebral and intracranial haemorrhage
Eye disorders	
Common	Eye haemorrhage (including conjunctiva haemorrhage)
Cardiac disorde	rs
Common	tachycardia
Vascular disord	ers
Common	hypotension, haematoma
Not known	Pseudoaneurysm formation following percutaneous intervention

common Epistaxis				
uncommon Haemoptysis	Haemoptysis			
Gastrointestinal disorders				
Common Gastrointestinal tract haemorrhage (incl. gingival bleeding a haemorrhage), gastrointestinal and abdominal pains, dyspepsi constipation, diarrhoe, vomiting				
Uncommon Dry mouth				
Hepatobiliary disorders				
Uncommon Hepatic function abnormal				
Rare Jaundice				

Skin and subcuta	neous tissue disorders
Common	Pruritus (incl. uncommon cases of generalized pruritus), rash, ecchymosis
Uncommon	Urticaria, cutaneous and subcutaneous haemorrhage
Musculoskeletal	and connective tissue disorders
Common	Pain in extremity
Uncommon	Haemarthrosis
Rare	Muscle haemorrhage
Unknown	Compartment syndrome secondary to a bleeding
Renal and urinar	y disorders
Common	Urogenital tract haemorrhage (incl. haematuria and menorrhagia)
Uncommon	Renal impairment (incl. blood creatinine increased, blood urea increased)
Unkown	Renal failure / acute renal failure secondary to a bleeding sufficient to cause hypoperfusion
General disorder	s and administration site conditions
Common	Fever, peripheral oedema, decreased general strength and energy (ind. fatigue and asthenia)
Uncommon	Feeling unwell (incl. malaise), localized oedema

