#### 6.3 Hypothesis Testing

Unless otherwise specified all hypotheses will be tested at a 5% level of significance against two-sided alternative hypotheses.

Continuous variables will be analyzed by the following test procedures:

First of all the assumption of normally distributed data will be checked with Shapiro-Wilk test by treatment group. If the hypothesis of normally distributed data cannot be rejected for both treatment groups treatments will be compared by an ANCOVA procedure which includes "treatment" as the main factor and "baseline value" as covariate. T-Tests for independent samples will be used to compare groups at baseline.

In the event that the normality assumption is not warranted, data will be log-transformed and normality assumption of the transformed data will be checked by Shapiro-Wilk test. In case of non-rejection of the hypothesis of normally distributed data for both treatment groups, ANCOVA procedure and t-tests as described above will be performed on the basis of log-transformed data.

Point estimates and 95% CI of the difference in (adjusted) mean change from baseline will be provided if data are evaluated on basis of an ANCOVA procedure.

Otherwise Mann-Whitney's-U test on the basis of original data will be applied for comparison of groups at baseline. Mann-Whitney's-U test on the basis of intra-individual differences to baseline will be applied for treatment comparison per visits after baseline. Wilcoxon's signed rank test will be applied to evaluate changes from baseline per treatment group.

Categorical variables with 2 categories will be analyzed using Fisher's exact test (with Yates correction) to compare proportions between treatment groups. Variables with more than 2 categories will be compared by Pearson's Chi-square test. Additionally for each category, the proportions of treatment groups are compared using an (asymptotic) z test. Significant differences in proportions will be flagged, p-values for the z-test will not be shown.

Missing values will not be imputed.

If necessary, modifications of this general procedure will be described in the following sections of chapter 6.

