#### 7.8.3 Adverse Events

				Comparison of					
Adverse Events			Total		Rivaroxaban		spirin	Proportions	
		N	%	N	%	Ν	%	p-Value	
Number of	AE								
	SAE								
Patients	ADR								
	SADR								
	AE							-	
Number of Events	SAE								
	ADR								
	SADR								

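### SAP table 7.8.3 tests ADR and SADR proportions between arms although ADR status rests on an unblinded yes/no causality call, so unequal attribution alone can give a nominally significant ADR difference (minor)

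*Protocol*

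**What the plan says.** - **Blinding.** Protocol 5.10: "Not applicable, open-label study".
- **How an event becomes an ADR.** Under Protocol 10.2.1 the investigator assesses every AE and SAE and answers the relatedness question yes or no. The rule begins "An ADR/SADR is suspected if the causal relationship is assessed as" and is completed by a yes. SAP 4.7.3 carries the same binary variable.
- **What is tested.** The SAP mock-up headed "7.8.3 Adverse Events" has a column comparing proportions with a p-value. Its patient-level rows are AE, SAE, ADR and SADR. SAP 6.3 assigns Fisher's exact test to two-category variables "to compare proportions between treatment groups", two-sided at 5%. The text of SAP 6.12.3 mentions only listings and incidences, so the ADR and SADR tests come from 6.3 together with the mock-up.
- **Second assessment.** Protocol 10.2.3 requires a separate sponsor assessment of causality, for SAEs only. The SAP does not say whether the investigator's or the sponsor's judgement is tabulated.
- **Reference information.** Protocol 10.4.1 says "For this study, the applicable reference document is the most current version of the SmPC" and continues "The expectedness of AEs will be determined by the sponsor according to the applicable reference document". The safety summary that follows opens "The majority of adverse reactions reported for Xarelto", and Table 11 lists reactions for that product only. Aspirin is also an IMP (Protocol 5.3: "The IMP ASS 100 TAH of the control group will be preferably used from ratiopharm GmbH"), but the protocol prints only its indications and contraindications.

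**The concern.** The proportion of patients with an ADR is the product of two things: how often patients have an event, and how readily someone who knows the arm calls it drug-related. A p-value on that product cannot separate more harm from readier attribution. Neither document provides a blinded or independent causality review of non-serious events, so the plan has nothing to prevent or detect an attribution gap.

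At stake is the interpretation of one safety table. SAP 2.3.3 lists a risk-benefit assessment among the explorative objectives. A significant ADR row could be read there as excess harm of one drug when event rates are equal. Equally, harm of the other drug that was not attributed would not appear in that row. The primary endpoints are not affected.

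**Working it through.** **Arm size.** The documents give no AE, ADR or attribution rate and no power for safety, so the only planned figure to reproduce is the arm size. Protocol 9.1.8 has a difference of 1.2, SD 2.4, one-sided 5% and 90% power:

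n per arm = 2(1.645 + 1.282)² × (2.4/1.2)² ≈ 68.5, so 69.

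The exact t calculation needs 70 per arm (power 0.903). That is 140 in total, and 140/0.75 gives 187. The plan's 141 evaluable patients give 141/0.75 = 188, or 94 per arm. The figure reproduces. The safety set can hold at most 94 per arm, and 94 is used below.

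**Model.** Let p be the true proportion of patients with an AE, the same in both arms. Let q1 and q2 be the probabilities that a patient with an AE has at least one called related. The ADR rate in arm i is p × qi. The rejection probability is the sum, over all pairs of counts (a, b) with two-sided Fisher p < 0.05, of Bin(a; 94, p·q1) × Bin(b; 94, p·q2). All values of p and q are assumptions.

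**ADR: percentage of trials with p < 0.05**

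| AE rate, both arms | q 20% vs 20% | 30% vs 20% | 40% vs 20% | 50% vs 20% |
|---|---|---|---|---|
| 30% | 2.3 | 7.4 | 21.9 | 43.5 |
| 50% | 2.8 | 12.8 | 41.4 | 73.3 |
| 70% | 3.1 | 19.1 | 60.1 | 90.4 |

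For example, with p = 50% and q = 40% vs 20%, the ADR rates are 0.5 × 0.4 = 20% and 0.5 × 0.2 = 10%, and the test rejects in 41.4% of trials. The arms are of equal size and the test is two-sided, so exchanging the arms leaves these percentages unchanged.

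**Counts that reach significance.** 15 vs 5 patients with an ADR, or 21 vs 10, gives p < 0.05.

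**Contrast.** With a true AE rate of 50% in both arms, the all-causality AE row rejects in 3.4% of trials.

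**SADR, assumed SAE rate 10% in both arms**

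| q | SADR rates | p < 0.05 |
|---|---|---|
| 20% vs 20% | 2% vs 2% | 0.4% |
| 40% vs 20% | 4% vs 2% | 3.8% |
| 60% vs 20% | 6% vs 2% | 15.3% |
| 50% vs 10% | 5% vs 1% | 16.8% |

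The two-fold gap that matters for ADR leaves the SADR test below its nominal 5%. Only wider gaps exceed it.

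**The case against.** **The one-sided reaction list is not the mechanism.** A reader might infer that Table 11 makes investigators attribute more events to rivaroxaban. The documents do not support this. The list stands under expected adverse events, and expectedness is a sponsor decision. The causality rule in Protocol 10.2.1 points to unexplained laboratory findings, dechallenge and rechallenge, and timing; it mentions neither the list nor the SmPC. The list could at most prime investigators. They are also told of aspirin's risks: the contraindications in 5.3.2 include bleeding and ulceration, and 5.11 and 5.11.1 discuss bleeding with aspirin. This objection stands.

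**Section 10.4.1 does not limit the reference document to rivaroxaban.** It names no product. Protocol 10.1 refers to the product information for the IMP, both drugs are IMPs, and 5.9 refers to an SmPC for aspirin. Naming a document for each product would be a clarification and does not carry this point. This also stands.

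**Comparisons that need no causality call are already planned.** Table 7.8.3 tests AE and SAE, and table 7.8.4 tests bleeding on definitions that do not ask about causality. This stands and limits the consequence. AE reporting in an open-label trial can itself differ by arm, so those rows are less exposed rather than immune.

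**The sizes are illustrative.** The 41% figure needs a two-fold attribution gap that no document supports; 30% vs 20% gives 13%. A reader might also infer that false results would fall on rivaroxaban, but the direction is assumed. It would likewise go too far to say that the ADR row measures attribution only, since it also reflects how often events occur.

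**What remains.** The ADR and SADR rows carry the same kind of p-value as the all-causality rows, ADR status is an unblinded judgement, and the SAP does not say whose judgement is used.

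**Conclusion.** The point holds as a minor one. Following the SAP exactly can give a nominally significant ADR difference from unequal attribution when true AE rates are equal. At an assumed AE rate of 50% and 94 per arm, the frequency is about 13% for attribution of 30% vs 20% and about 41% for 40% vs 20%, against about 3% with equal attribution. These figures show what the test permits; they do not predict what this trial will find.

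The same conclusion should not be extended to SADR with equal force. At an assumed 10% SAE rate and 40% vs 20% attribution the rejection rate is about 4%, and SAEs receive a separate causality assessment by the sponsor.

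**What to change.** In SAP 6.12.3 and table 7.8.3:

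1. State that between-arm inference on harm rests on the AE and SAE rows regardless of causality, and on bleeding table 7.8.4.
2. Keep the ADR and SADR rows as descriptive counts and percentages by arm, without p-values.
3. Add a table note that causality was judged unblinded.
4. State whether the investigator's or the sponsor's causality assessment is tabulated.

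One detail needs settling with item 1. SAP 4.7.3 places a patient with any SAE in the SAE category and leaves the AE category to patients whose events were never serious. If that rule carries into table 7.8.3, the AE row is not a count of patients with any AE and should be redefined as one.

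The cost is a few lines of SAP text and two p-values fewer in one table. No new data are needed. The downside is that there is no formal test of investigator-attributed events.
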